8.4 Withdrawal of individual subjects

Subjects can leave the study at any time for any reason if they wish to do so without any consequences. The investigator can decide to withdraw a subject from the study for urgent medical reasons. When participants decide to withdraw their participation, they will be asked to participate in 'early-term assessments'.

After subjects have entered the study, participation will be stopped in case of occurrence of any of the following:

- Participants own decision
- The occurrence of an AE or clinically significant laboratory change or abnormality that, in the judgment of the investigator, warrants withdrawal of the study
- Subjects need medical procedures that are not allowed in the protocol
- Subjects cannot undergo the procedures to investigate the research questions as outlined in this protocol
- Non-compliance
- In addition to these requirements for study drug discontinuation, the investigator should discontinue study participation for a given subject if, on balance, he thinks that continuation would be unbeneficial to the subjects well-being

8.4.1 Specific criteria for withdrawal (if applicable)

Not applicable

8.5 Replacement of individual subjects after withdrawal

Participants will be replaced to maintain sufficient power.

8.6 Follow-up of subjects withdrawn from treatment

If patients withdraw from the study, vital signs will be collected and recent history to confirm safe withdrawal from the study. There is no harm in suddenly stopping study medication, although glucose levels may increase mildly.

8.7 Premature termination of the study

I do not expect premature termination of the study. No interim analysis for efficacy is performed. Ertugliflozin is a drug with a well-established safety profile, and no new side effects are expected to be found in this study with 2 blocks of 10 days of active treatment. Obviously, if SAE are encountered that may be related to the study medication, a careful decision will be made to halt the study prematurely.

9. SAFETY REPORTING

9.1 Temporary halt for reasons of subject safety

In accordance to section 10, subsection 4, of the WMO, the sponsor will suspend the study if there is sufficient ground that continuation of the study will jeopardise subject health or safety. The sponsor will notify the accredited METC without undue delay of a temporary halt including the reason for such an action. The study will be suspended pending a further positive decision by the accredited METC. The investigator will take care that all subjects are kept informed.

9.2 AEs, SAEs and SUSARs

9.2.1 Adverse events (Aes)

Adverse events are defined as any undesirable experience occurring to a subject during the study, whether or not considered related to [the investigational product / trial procedure/ the experimental intervention]. All adverse events reported spontaneously by the subject or observed by the investigator or his staff will be recorded.

9.2.2 Serious adverse events (SAEs)

A serious adverse event is any untoward medical occurrence or effect that

- results in death;
- is life threatening (at the time of the event);
- requires hospitalisation or prolongation of existing inpatients' hospitalisation;
- results in persistent or significant disability or incapacity;
- is a congenital anomaly or birth defect; or
- any other important medical event that did not result in any of the outcomes listed above due to medical or surgical intervention but could have been based upon appropriate judgement by the investigator.

An elective hospital admission will not be considered as a serious adverse event.

Because this study is considered to be low-risk, as agreed by the Ethical Committee, SAE's will be recorded and reported yearly through the web portal ToetsingOnline to the accredited METC that approved the protocol.

9.2.3 Suspected unexpected serious adverse reactions (SUSARs)

Adverse reactions are all untoward and unintended responses to an investigational product related to any dose administered.

Unexpected adverse reactions are SUSARs if the following three conditions are met:

1. the event must be serious (see chapter 9.2.2);
2. there must be a certain degree of probability that the event is a harmful and an undesirable reaction to the medicinal product under investigation, regardless of the administered dose;
3. the adverse reaction must be unexpected, that is to say, the nature and severity of the adverse reaction are not in agreement with the product information as recorded in:
 - Summary of Product Characteristics (SPC) for an authorised medicinal product;
 - Investigator's Brochure for an unauthorised medicinal product.

The sponsor will report expedited the following SUSARs through the web portal *ToetsingOnline* to the METC

- SUSARs that have arisen in the clinical trial that was assessed by the METC;
- SUSARs that have arisen in other clinical trials of the same sponsor and with the same medicinal product, and that could have consequences for the safety of the subjects involved in the clinical trial that was assessed by the METC.

The remaining SUSARs are recorded in an overview list (line-listing) that will be submitted once every half year to the METC. This line-listing provides an overview of all SUSARs from the study medicine, accompanied by a brief report highlighting the main points of concern.

The expedited reporting of SUSARs through the web portal Eudragilance or *ToetsingOnline* is sufficient as notification to the competent authority.

The sponsor will report expedited all SUSARs to the competent authorities in other Member States, according to the requirements of the Member States.

The expedited reporting will occur not later than 15 days after the sponsor has first knowledge of the adverse reactions. For fatal or life threatening cases the term will be maximal 7 days for a preliminary report with another 8 days for completion of the report.

The site at Colorado University (PI [name]) will report all SAEs and SUSARs to the local competent authority according to the requirements of that Member State. In addition, they will inform the sponsor/coordinating investigator of the study ([name]) and MSD within a single day.

Please describe also the method of breaking the code for SUSAR reporting:

The pharmacy of each participating center performs the randomisation of subjects to the treatment categories. In the event of an emergency, the local pharmacy provides the local researcher with information concerning the treatment of the subject of the SUSAR. Unblinding is not to be performed for any reason other than an emergency where unblinding is required and should be reported in the CRF. The local investigator must also immediately inform the project leader and the principal investigator about the unblinding procedure. If it does not compromise the welfare of the participant, a close-out visit which includes drawing of blood samples for safety or pharmacodynamic assessments will be performed.

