Throughout the study duration, all study personnel will remain blinded with regard to the medication used. The randomization –in order to achieve blinding for study personnel- will be performed by the trial pharmacist of the Amsterdam UMC-VUmc. The investigator will receive the subjects blinding information concerning the study medication in the form of a sealed envelope; this envelope will be stored on a secure location in the Diabetes Center Amsterdam UMC-VUmc. The blind shall not be broken by the investigator unless information concerning the study medication is necessary for the medical treatment of the subjects. Procedures regarding emergency unblinding are described in Chapter 9. If the investigator is unblinded, study medication will be stopped immediately in addition to the withdrawal of the study subject from the study. At the end of the study, following the last patients last visit and database lock (which will only occur after medical / scientific review), the blind will be broken by the trial pharmacist.

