8.2 Randomisation, blinding and treatment allocation

The study is blinded with ertugliflozin and matching placebo's being provided by MSD. The investigator will send a computer-generated randomization list (block randomization of 4) via an automated system (Castor EDC) to the trial pharmacy of Amsterdam UMC. In this way, all study participants and trial personnel remain blinded at all times. Unblinding will only occur in a medical emergency. The sodium diets are

of course open label. Each participant receives sufficient tablets (ertugliflozin or matching placebo) for each treatment period of n=10 days.

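### The SUSAR section describes only an emergency code break, so a non-emergency SUSAR must be reported without showing whether the block was ertugliflozin or placebo

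*Combined protocol and SAP*

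**What the plan says.** The template prompt at the end of section 9.2.3 is explicit: "Please describe also the method of breaking the code for SUSAR reporting". The reply gives one route: "In the event of an emergency, the local pharmacy provides the local researcher with information concerning the treatment of the subject of the SUSAR". It then closes the others: "Unblinding is not to be performed for any reason other than an emergency where unblinding is required".

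Other sections bear on the same question:

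- **Section 8.2** repeats the limit: "Unblinding will only occur in a medical emergency". On who is kept blind it says: "In this way, all study participants and trial personnel remain blinded at all times".
- **Section 6.8 (Blinding and Unblinding)** restricts the investigator: "The blind shall not be broken by the investigator unless information concerning the study medication is necessary for the medical treatment of the subjects". It attaches a consequence: "If the investigator is unblinded, study medication will be stopped immediately in addition to the withdrawal of the study subject from the study". It refers to chapter 9 for the emergency procedure and has the trial pharmacist break the blind after the last visit and database lock.
- **Section 8.7** says: "if SAE are encountered that may be related to the study medication, a careful decision will be made to halt the study prematurely". It does not mention the allocation.
- **Section 9.2.3** sets the expedited deadline at 15 days, or 7 plus 8 days for fatal or life-threatening cases, and describes the half-yearly line-listing as covering SUSARs attributed to the study medicine.

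A data safety monitoring board appears only in the list of abbreviations.

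**The concern.** The question in section 9.2.3 is about reporting; the answer is about treating a patient in an emergency. These are different needs. A serious, unexpected event may already be treated or resolved, or its care may not depend on the code. Such an event meets the reporting criteria but not the condition for unblinding.

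The text does more than omit a detail. It forbids unblinding for any other reason, so a pharmacist following it would have to refuse the allocation to whoever files the report. The ethics committee and competent authority would then receive a report of a suspected reaction to ertugliflozin that might describe a placebo block, with no means in the protocol of finding out until after database lock. Section 9.2.2 sends ordinary SAEs to the ethics committee only yearly, so the expedited SUSAR report is the fast safety channel for this trial.

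What is at stake is the correct attribution of a small number of serious events. Efficacy is not involved.

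**Working it through.** **1. Is there any other route to the allocation?** The sections, set side by side:

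| Section | Who may learn the allocation | When |
|---|---|---|
| 9.2.3 | Local researcher, from the local pharmacy | Emergency requiring unblinding |
| 8.2 | Not stated | Medical emergency |
| 6.8 | Investigator | When needed to treat the participant |
| 6.8 | Blind broken by the trial pharmacist | After last visit and database lock |
| 8.7, 9.1, 9.3 | No provision | – |

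Section 6.8 binds the investigator only, so on its own it would not stop a pharmacy telling a regulator. Sections 8.2 and 9.2.3 are worded without that limit and do stop it. The only planned later release comes after database lock, which has no link to the 15-day or 7-plus-8-day deadlines. No section gives the allocation to a safety function, a board, the ethics committee or the competent authority for a non-emergency SUSAR.

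**2. How much does the missing allocation matter?** The protocol gives no figure on this point, so there is none to reproduce. Inputs: four blocks per participant, two of them active (sections 3 and 8.7), 10 tablet days per block (section 8.2), and 34 participants (section 4.4).

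- Per participant: 2 × 10 = 20 ertugliflozin days and 2 × 10 = 20 placebo days; placebo share 20/40 = 50%.
- Whole trial: 34 × 20 = 680 days on each, so 680 of 1,360 tablet days are placebo.

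If serious events occur on ertugliflozin at R times the placebo rate, and are spread evenly over tablet days, the share falling in placebo blocks is 1/(1 + R). R is an assumption; the documents give no value.

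| R | Placebo share of serious events during dosing |
|---|---|
| 1 | 50% |
| 1.5 | 40% |
| 2 | 33% |
| 3 | 25% |

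These shares follow from the 2:2 block design and the assumed R. They show that the allocation carries real information about any one event. They do not say how many events there will be.

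**3. How many events?** No SAE or SUSAR rate is given. Exposure is small: 680/365.25 = 1.9 patient-years on ertugliflozin and the same on placebo. For scale only, section 13.1 puts euglycaemic ketoacidosis in type 2 diabetes at about 1 per 1,000 patient-years, which gives 1.9/1,000 = 0.002 cases. That is a recognised effect of the class and not a SUSAR rate, but it shows why few qualifying events are likely.

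**4. Does anything else move?** The sample size (34 completers, 4 mmHg difference, SD 8 mmHg) and the primary analysis do not use the unblinding rule and are unaffected.

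**The case against.** The strongest reply is that the protocol's safety judgements can be made blind. Section 9.2.3 asks only for some likelihood that the product caused the event, and compares the event's nature and severity with the product information. Both can be done by treating the tablet as possibly active. This stands: blinded causality assessment by the investigator is normal practice. It does not answer the point, which is that nobody who files or receives the report may learn the allocation either.

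A reader might infer that every halt decision under section 8.7 is taken blind and that placebo events will be counted as ertugliflozin toxicity. The documents do not support that. If the triggering event is an emergency requiring unblinding, section 9.2.3 releases the code and has the project leader and principal investigator told of the unblinding. Section 8.7 calls for a considered decision and is not a count with a threshold. Section 9.1 obliges the sponsor to suspend for a threat to safety whatever its cause, so a serious event on placebo plus a high-sodium diet may properly be weighed.

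A reader might also infer that any release of the allocation must unblind an endpoint assessor and cost the trial a participant. That the local researcher assesses endpoints is an inference. The primary endpoint is recorded by an ambulatory device, drop-outs are replaced (sections 4.4 and 8.5), and a participant with a serious suspected reaction might be withdrawn in any case under section 8.4.

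Finally, few such events are likely. That also stands, and it limits the importance of the point without removing it: the prohibition is explicit and the correction costs almost nothing.

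**Conclusion.** The point holds in a limited form. As written, a SUSAR that is not an emergency requiring unblinding must be reported and line-listed without its allocation, although 20 of each participant's 40 tablet days are placebo. Section 9.2.3 poses the question and does not answer it, and together with section 8.2 it forbids the obvious answer.

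The consequence is confined to attribution in safety reporting. The documents do not show that a SUSAR cannot be classified blind, that halt decisions are generally blind, or that events will in fact be misattributed. The 50% share rests on the block design and on events unrelated to the drug being spread evenly over tablet days; with an event rate on ertugliflozin up to three times that on placebo it would fall to 25%. No expected number of events can be stated. This is a gap worth closing, but it does not threaten the trial's conclusions.

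**What to change.** In section 9.2.3, leave the emergency route as it is and add a reporting route. For every suspected SUSAR, emergency or not, the pharmacy that holds the code supplies the allocation for the block concerned directly in the expedited report to the ethics committee and competent authority. The local researcher, outcome assessors and analysts stay blinded. Adjust section 8.2 so that its emergency-only wording admits this release.

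Two reconciliations belong with the edit:

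- **Who holds the code.** Sections 6.8 and 8.2 place the allocation with the Amsterdam pharmacy; section 9.2.3 says the pharmacy of each centre performs the randomisation; section 6.8 also gives the investigator a sealed envelope. Until this is settled, it is unclear who could supply the allocation for a Colorado participant.
- **Withdrawal and halt wording.** Sections 6.8, 8.7 and 9.2.3 should be reconciled on how a release that does not unblind the investigator relates to the existing text on withdrawal and on halting the study. No new stopping or withdrawal rule is proposed here.

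The added route has limits. It does not reach expected related SAEs under section 8.7, or events judged unrelated, so it should not be presented as informing every halt decision.

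The cost is a few sentences and one reporting step for the pharmacy per SUSAR. No committee or additional staff is needed.

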9.3 Annual safety report

In addition to the expedited reporting of SUSARs, the sponsor will submit, once a year throughout the clinical trial, a safety report to the accredited METC, competent authority, and competent authorities of the concerned Member States.

This safety report consists of:

- a list of all suspected (unexpected or expected) serious adverse reactions, along with an aggregated summary table of all reported serious adverse reactions, ordered by organ system, per study;
- a report concerning the safety of the subjects, consisting of a complete safety analysis and an evaluation of the balance between the efficacy and the harmfulness of the medicine under investigation.

9.4 Follow-up of adverse events

All AEs will be followed until they have abated, or until a stable situation has been reached. Depending on the event, follow up may require additional tests or medical procedures as indicated, and/or referral to the general physician or a medical specialist. SAEs need to be reported till end of study within the Netherlands, as defined in the protocol.

10. STATISTICAL ANALYSIS

Sample size calculations

The primary endpoint of the study is to investigate the modifying effects of WHO-recommended sodium intake (90 mmol per day) vs. high sodium intake (targeted at 250 mmol per day) on the effect of ertugliflozin 15 mg daily, versus placebo, on 24-hour blood pressure in overweight/obese adults with type 2 diabetes.

Based on previous studies in patients treated with SGLT2 inhibitors, we expect a change in systolic blood pressure of 6-8 mmHg during normal sodium intake (150 mmol/day) [PMID: 33318125; PMID: 23668478]. Based on our hypothesis, this effect is increased on a low-sodium intake and reduced during high-sodium intake.

We expect a difference of 4 mmHg between the placebo-controlled effects of ertugliflozin on a low- versus high-sodium diet, with a conservative SD on this difference of 8 mmHg.

A total of 34 patients completing the study provide 80% power at a two-sided alpha of 0.05, to detect a 4 mmHg difference with the indicated SD of 8 mmHg. Drop-outs will be replaced. Based on the RED study and DAPASALT study, the power needed to detect changes in eGFR and hematocrit are of sufficient magnitude and therefore we expect sufficient power for these parameters as well. The calculation is based on a paired design. The sample size was calculated using Stata-Software (v. 11.2, College station, TX, USA).

10.1 Primary study parameter(s)

General considerations

1. All tests of differences between treatments will be conducted at a two-sided significance level of <0.05 . In general, the null hypothesis (H_0 : no difference exists between treatment with the study drug and placebo) intervention) will be tested against the hypothesis H_1 : a difference exists between treatment with the study drug and placebo), with respect to the underlying parameter of interest.
2. All variables will be expressed as mean \pm SEM when normally distributed, or –in case of non-normal distribution- be expressed as median and interquartile range (IQR). Log transformation will be applied to obtain normal distribution as appropriate for the statistical tests.

3. In case of missing data, a multiple imputation technique will be applied and compared with complete case analysis.

Analysis population

The efficacy analysis population will be based on the per protocol (PP) principle – i.e. all subjects who completed the entire treatment period using the treatment as originally allocated. Safety analysis will be performed in all patients who received one or more doses of the study medication.

Statistical analysis of study endpoints

We will use a two-way ANOVA to evaluate the main effects of diet and treatment as well as an interaction between ertugliflozin vs. placebo during high and low-sodium intake on the main outcomes. Appropriate covariates may be added to the model. Because of the crossover design of our trial, we will assess the carryover effect by including the sequence allocation as a factor in the mixed model. If a carryover effect will be detected ($p < 0.1$), only the first study period will be analysed (treating it as a parallel randomised controlled trial).

For possible confounders, we will test whether there is an association with both the dependent and independent variable ($p < 0.1$). If this is the case, this confounder will be added to the model as covariate. Since all outcome variables – primary, secondary and exploratory – are continuous, this statistical technique can be applied.

The large amount of secondary/exploratory endpoints potentially justifies the use of corrections for multiple tests. However, there is an increasing debate on whether this should be done, because of the increased risk of type 2 errors which could lead to prematurely discarding of potential useful observations (Rothman, 1990). As recently pointed out (Streiner & Norman, 2011), in a hypothesis-generating study – such as the current study – correction for multiple outcomes can be detrimental.

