4.3 Exclusion criteria

A potential subject who meets any of the following criteria will be excluded from participation in this study:

- History of unstable or rapidly progressing renal disease

- Estimated GFR <60 mL/min/1.73m² or eGFR > 90 mL/min/1.73m² determined by CKD-EPI
- UACR > 30 mg/mmol
- Current/chronic use of the following medication: SGLT2 inhibitors, TZD, GLP-1RA, glucocorticoids, immune suppressants, antimicrobial agents, chemotherapeutics. Participants should be on a stable dose of antipsychotics, tricyclic antidepressants (TCAs) and monoamine oxidase inhibitors (MAOIs). Subjects on diuretics will only be excluded when these drugs cannot be stopped for the duration of the study.
- Chronic use of non-steroidal anti-inflammatory drugs (NSAIDs) will not be allowed, unless used as incidental medication (1-2 tablets) for non-chronic indications (i.e. sports injury, headache or back ache). However, no such drug can be taken within a timeframe of 2 weeks prior to renal testing
- History of diabetic ketoacidosis (DKA) requiring medical intervention (e.g. emergency room visit and/or hospitalization) within 1 month prior to the Screening visit.
- Current urinary tract infection and active nephritis
- Recent (<6 months) history of cardiovascular disease, including:
 - o Acute coronary syndrome
 - o Chronic heart failure (New York Heart Association grade II-IV)
 - o Stroke or transient ischemic neurologic disorder
- Severe hepatic insufficiency and/or significant abnormal liver function defined as aspartate aminotransferase (AST) >3x upper limit of normal (ULN) and/or alanine aminotransferase (ALT) >3x ULN
- Active malignancy. History of malignancy is allowed unless the participant still has active treatment other than hormonal therapy.
- History of or actual severe mental disease
- Substance abuse (alcohol: defined as >4 units/day)
- Allergy to any of the agents used in the study
- Individuals who are investigator site personnel, directly affiliated with the study, or are immediate (spouse, parent, child, or sibling, whether biological or legally adopted) family of investigator site personnel directly affiliated with the study
- Inability to understand the study protocol or give informed consent

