5.2 Use of co-intervention (if applicable)

During the treatment phases, participants will be subjected to a sodium diet. While a regular sodium intake in the Netherlands, based on previous studies and literature, is around 170 mmol/day; we will coach participants by providing food lists and counselling, to lower their intake to WHO-recommended amounts of 90 mmol/day. This will be done during 10 days prior to start study medication (compliance checked by 24-hour sodium analysis) and during the 10-day intervention. Thus for a total of 20 days per treatment block. Low-sodium intake will be effected during both ertugliflozin and placebo. Similarly, using dietary counselling, participants will be instructed to follow a high-sodium diet aimed at 250 mmol/day.

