During the infusion, several measurements will be performed including anthropometrics, bio-impedance analysis, blood pressure measurement and collection of samples for biomarker analysis.

	Day -10	Day -2	Day -1	Day 0	Day 3	Day 10
Start sodium-diet (continue until day 10)	X					
24-hr urine sodium (compliance)		X	X			
Start study medication (continue until day 10)				X		
Telephone call compliance					X	
Recent history						X
24-hr blood pressure						X
Measured GFR						X
ERPF						X
Intrarenal hemodynamic function						X
Office blood pressure						X
Hematocrit						X
Renal oxygenation (BOLD MRI)						X
RAAS components						X
Collection of biomarkers						X
Body anthropometrics						X
24-hr urine analysis (sodium, UACR)						X

Efficacy measurement more detailed:

- 1) **Height.** A height measuring board will be used to assess height. Patients will be asked to remove their footwear and headgear and to stand on the board with their feet together, heels against the back board and knees straight. The patient should be looking straight ahead, without tilting the head up, with eyes and ears at the same level. The measure arm will gently be moved down onto the head of the participant and height will be read in centimeters at the exact point.
- 2) **Weight.** Body weight will be recorded by a digital calibrated weighing scale on a firm, flat surface. Patient will be asked to remove their footwear, extra layers of clothing, jewelry and any items in his/her pockets before standing still on the weighing scale with arms placed on the side. Measurement will be recorded on the Case Report Form (CRF) to the nearest kilogram. No deduction for clothing will be permitted.
- 3) **Body Mass Index (BMI).** BMI will be derived from height and bodyweight by using the mathematical formula: $BMI = [kg/[m]^2]$.
- 4) **Waist circumference.** A constant tension tape will assess waist circumference with the patient in a standing position with the arms relaxed at the sides and without clothing, that is, directly over the skin. Measurement will be performed at the midpoint between the lower margin of the last palpable rib and the top of the iliac crest at the end of a normal expiration.

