13. STRUCTURED RISK ANALYSIS

13.1 Potential issues of concern

Study medication

Participants will receive ertugliflozin 15 mg, an SGLT-2 inhibitor which is approved for blood-glucose lowering treatment in T2DM patients, and based on currently available data, is considered to be safe. Furthermore, SGLT-2 inhibitors may have other beneficial effects in general and are associated with a decrease in blood pressure and body weight. In large-sized cardiovascular outcome study, ertugliflozin was shown to have beneficial effects on cardiovascular outcomes and chronic kidney disease.

The most common adverse effects for ertugliflozin are genital mycotic infections and to a lesser extent pruritus, polyuria, frequent voiding and nycturia. However, genital mycotic infections usually occur after prolonged treatment, at least weeks. For canagliflozin, not ertugliflozin, increased amputations were reported in one study, but not in people with kidney disease, mostly in people that had previous amputations.

Hypoglycemia: SGLT2 inhibitors do not cause hypoglycemia as they do not increase insulin secretion. In people without diabetes, SGLT2 inhibitors do not cause hypoglycemia. When combined with drugs as insulin and sulfonylurea, SGLT2 inhibitors may cause hypoglycemia, particularly in people with normal eGFR.

Keto-acidosis: this has been reported in people with type 1 diabetes,²⁸ but is rare in people with type 2 diabetes with only a few cases reported worldwide.²⁸

Sodium diet:

Participants will undergo two periods of increased sodium intake (of 20 days each). While higher sodium intake, may increase blood pressure, it is usually not associated with adverse effects. Of note, sodium intake in the Netherlands is really high, therefore, for some people it may be their normal intake. Lowering sodium intake is not related to any health risk.

a. Level of knowledge about mechanism of action

Regarding side effects, they have a well-defined mechanism of action:

1. Genitourinary mycotic infections: due to SGLT2-induced glucosuria, urine provides a better culture media for mycotic infections.
2. Hypoglycaemia: higher risk in people with concomitant insulin therapy and/or sulfonylurea. Due to glucosuria, the amount of circulation can be inappropriate leading to hypoglycaemia.

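### The safety population requires a tablet, so a participant who withdraws with an adverse event during the 10-day diet run-in of block 1 is left out of the safety analysis

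*Combined protocol and SAP*

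**What the plan says.** Section 10.1 (Analysis population) sets a per-protocol population for efficacy. For safety it says: "Safety analysis will be performed in all patients who received one or more doses of the study medication". No other safety population is defined.

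Section 3 lists four conditions, each pairing a diet with a tablet, and section 8.3 puts the four blocks in random order, so diet is randomised as well as drug. Section 5.2 gives the timing of the diet: "This will be done during 10 days prior to start study medication (compliance checked by 24-hour sodium analysis) and during the 10-day intervention". It adds: "Thus for a total of 20 days per treatment block". The schedule table in 8.3 agrees, with the diet starting on day -10 and the tablets on day 0. Section 5.2 treats the diet as a co-intervention, separate from the study medication.

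Withdrawal for an adverse event or for non-compliance applies once a subject has entered the study (8.4). On those who withdraw, 8.5 says: "Participants will be replaced to maintain sufficient power". Section 9.2.1 requires adverse events during the study to be recorded whether or not they are related to the intervention.

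**The concern.** A safety population normally begins with first exposure to anything the trial assigns. Here the first assigned exposure is the diet, but entry depends on the tablet. A participant who tolerates the first run-in goes on to a dose and is counted. One who has an event on the diet and leaves before day 0 is not. Inclusion therefore depends on the outcome being summarised.

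Leaving in this window is foreseeable: sodium compliance is checked on days -2 and -1, and non-compliance is a reason for withdrawal. The schedule in 8.3 shows no safety assessment between day -10 and day 0, and the safety item there is aimed at effects of the study medication. Reported adverse events are thus the main source of safety information on the diet-only phase.

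What is at stake is the completeness of a descriptive safety summary for one of the two randomised factors, in a population that may include people with hypertension (4.2) and for whom 13.1 accepts that higher sodium intake can raise blood pressure.

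**Working it through.** **The plan's own figure.** Sections 4.4 and 10 give 34 completers for a 4 mmHg difference, SD of the difference 8 mmHg, two-sided alpha 0.05, 80% power, paired design.
- Normal approximation: n = ((1.960 + 0.842) × 8/4)² = 31.4, rounded up to 32.
- Paired t-test (noncentral t): the smallest n with at least 80% power is 34, with power 80.8%.

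The stated 34 is reproduced. It counts completers, so the definition of the safety population does not affect it.

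**The uncovered window.** Inputs from 5.2 and 8.3: 4 blocks, each with 10 days of diet alone and 10 days of diet plus tablet.
- Planned diet days: 4 × 20 = 80.
- Diet days without tablets: 4 × 10 = 40.
- Diet days before the first tablet of the study: 10 (days -10 to -1 of block 1).

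Once a participant has taken one tablet, active or placebo, the criterion in 10.1 is met for the rest of the study. The run-ins of blocks 2 to 4 (3 × 10 = 30 days) are therefore covered. The uncovered window is 10/80 = 12.5% of planned diet days.

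**The share of people omitted.** Suppose 34 participants are dosed and k others withdraw in the window and are replaced. The safety analysis then holds 34 of the 34 + k who started a diet:

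| k | Omitted share k/(34+k) |
|---|---|
| 0 | 0% |
| 1 | 1/35 = 2.9% |
| 2 | 2/36 = 5.6% |
| 3 | 3/37 = 8.1% |
| 4 | 4/38 = 10.5% |

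If participants who drop out after dosing are also replaced, the denominator grows and these shares shrink a little.

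**How likely k ≥ 1 is.** The documents give no rate of withdrawal before the first dose. The rates p below are assumptions. Expected exclusions to reach 34 dosed are 34/(1-p) - 34; the chance of at least one among the first 34 is 1 - (1-p)^34.

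| Assumed p | Expected exclusions | Chance of at least one |
|---|---|---|
| 1% | 0.3 | 29% |
| 3% | 1.1 | 65% |
| 5% | 1.8 | 83% |
| 10% | 3.8 | 97% |

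These count all withdrawals before the first dose. Those with an adverse event are a subset.

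**Direction.** If x of the 34 dosed and all k omitted participants have an event, the reported proportion is x/34 and the full one is (x+k)/(34+k). The difference is k(34-x)/(34(34+k)), which is never negative. If some of the k left without an event, the event count is still never too high, although the proportion need not be too low.

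**The case against.** The best defence is that nothing is lost from the record. Adverse events are recorded regardless of dose or relatedness (9.2.1), serious ones go to the ethics committee (9.2.2), events are followed until they resolve or stabilise (9.4), and those who withdraw have vital signs and history taken (8.6). No safety endpoint is listed in 8.1 and no comparative test of diet safety is planned. All of this stands. It confines the problem to one descriptive analysis, but it does not bring an undosed participant into that analysis.

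A reader might also infer more than the documents support:
- **That all 40 diet-only days are unprotected.** They are not; 30 of them follow the first tablet.
- **That the rule biases a conclusion that the diet is safe.** The statement in 13.2 that the diet carries no risk belongs to a risk analysis written before any data, so the analysis population cannot have shaped it.
- **That replacement removes people from the safety analysis.** It does not. A replaced participant who took one tablet stays in; only the dose criterion excludes.
- **That some participants start the diet just after stopping a diuretic.** Section 4.3 says: "Subjects on diuretics will only be excluded when these drugs cannot be stopped for the duration of the study". It gives neither the timing of stopping relative to day -10 nor the number affected.

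**Conclusion.** The point holds, at a modest size. The rule in 10.1 leaves out people exposed to a randomised intervention, and no other section corrects it. It applies only to the block 1 run-in, 10 of 80 planned diet days. The number of people concerned is unknown and may be zero; the percentages above rest on assumed values of k and on exactly 34 dosed participants. Where such a participant had an event, the safety summary can only understate diet-related harm. In a study of 34, even one omitted participant is a visible part of a safety table. The primary analysis and the sample size do not change. The wording gap is certain; whether it will matter in this trial is not.

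**What to change.** In 10.1, define the safety population as all participants who started an assigned sodium diet or took at least one dose of study medication, including those later replaced. This wording is enough. Extending it to anyone who had a study procedure would bring in screening failures, who have blood tests and an ECG under 8.3 but are never assigned a diet.

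Tabulate adverse events by condition and by phase: diet only, diet plus tablet, and washout. Report the number who withdrew before the first dose, even if it is zero.

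The cost is one sentence and one extra table. No new data are needed, since the events are already recorded under 9.2.1, assuming that onset dates are captured with them. Conduct of the trial and clinical management do not change.
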